13.5.2. Study Population

Extent of exposure

- Number of days of exposure to study drug will be calculated based on the formula: Duration of Exposure in Days = (Treatment Stop Date – Treatment Start Date) + 1
- Participants who were randomised but did not report a treatment start date will be categorised as having zero days of exposure.
- The cumulative dose will be based on the formula: Cumulative Dose = Sum of (Number of Days x Total Daily Dose)
- If there are any treatment breaks during the study, exposure data will be adjusted accordingly.
- Average dose is the cumulative dose divided by the duration of exposure.

207546

13.5.3. Pharmacokinetics

Monocyte concentration

• In addition to the intracellular GSK3206944 raw concentration, x, which is measured as ng per mL in reagent, it will be also derived the molar concentration within the monocytes, y, which is:

 $y(nM) = x(ng/mL)/MMV/MW/20*10^{9}$

where the mean monocyte volume (MMV) is equal to 261 fL which is derived from the average of 150^a, 250^a, 480^a, 167^b fL reported in literature,

the molecular weight (MW) is equal to 468.6 (see Technical Evidence Document) and assuming that 20 is the number of millions of cells per mL of reagent. In practical terms this is equivalent to y(nM) = x(ng/mL)*408.8154.

^a https://www.ncbi.nlm.nih.gov/pubmed/7354131 ^b https://www.sciencedirect.com/science/article/pii/S0009898118301311#f0005

13.5.4. Pharmacodynamic

Percent inhibition

- The percentage inhibition (Truculture assay), to be calculated for select biomarkers, is defined as the reduction from baseline in %, e.g. a 15% reduction from baseline would be a 15% inhibition.
- The predicted percentage inhibition (y) in undiluted samples, to be calculated for selected biomarkers, from the above percentage inhibition (z(%)) in the 3-fold diluted samples of Truculture assay as:

$$y(\%) = \frac{100}{1 + \left(\frac{1}{DF}\right)^{hill} * \frac{100 - z(\%)}{z(\%)}}$$

where the dilution factor (DF) is equal to 3

Hill coefficient (hill) is equal to 1.4

The above formula assumes that the in vivo-inhibition versus PK concentration follows the in vitro Emax model relationship with the same concentration generating 50% effect, ec50, and the same hill coefficient and same Emax=1. In fact from

$$z(\%) = \frac{x^{hill}}{x^{hill} + ec50^{hill}} \cdot 100$$

it is possible to derive

$$ec50^{hill} = \frac{x^{hill} \cdot 100 - z(\%) \cdot x^{hill}}{z(\%)}$$

and substituting $ec50^{hill}$ in the equation of undiluted samples, where the ec50 is DF fold lower we obtain:

$$y(\%) = \frac{x^{hill}}{x^{hill} + \left(\frac{ec50}{DF}\right)^{hill}} \cdot 100 = \frac{x^{hill}}{x^{hill} + \frac{x^{hill} \cdot 100 - z(\%) \cdot x^{hill}}{DF^{hill} \cdot z(\%)} \cdot 100$$

which, after simplification by x^{hill} , results in the above equation

207546

Biomarkers

Biomarker Code (BICATCD), Biomarker Test Code (BITESTCD), Biomarker Testing Method Code (BIMETHCD) and Units of Measurement (BIORRESU) are summarised below.

Name (Analyte)	Biomarker Description	BICATCD	BITESTCD/ BIMETHCD/ BIORRESU	SAC ENDPOINTS
Soluble Inflammatory Mediators (Blood)	Interleukin 6	IL6	CONC/ ECLIA/ PG/ML	S4
TruCulture	Monocyte chemotactic protein-1	MCP1	CONC/ ECLIA/ PG/ML	S4
	Tumour necrosis factor alpha (TNF-α)	TNFA	CONC/ ECLIA/ PG/ML	S4

207546

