5.5.4. Human PK and PK/PD predictions

The PK of GSK3358699 in humans has been predicted by PBPK modelling using software Gastroplus. The human PBPK model was based on scaling of the monkey parameters, hepatic and renal clearance, except for the human acid metabolite (GSK3206944) liver clearance which was based on scaling of the dog *in vivo* liver clearance. Based on this model a compartment model was built for selecting doses and predicting exposures (see Section 5.5.1).

[figure not shown]
LPS-induced MCP-1 inhibition is considered a robust measurement of BET protein target engagement. Human predicted MCP-1 inhibition levels (Figure 5) were based on results from *in vitro* human whole blood assay (LPS stimulated) data which provided an estimated pIC₅₀ of 8.13, which translates to a plasma IC₅₀ of 4.8 ng/ml and a plasma IC₉₀ of 22.9 ng/ml (Hill slope=1.4).

As shown in Figure 4, Figure 5 and Table 2, the doses of GSK3358699 to be explored as part of the FTIH study have been carefully modelled to ensure a controlled dose escalation, such that the Brd4 BD1 IC₅₀ (25 ng/ml) is only exceeded at small multiples and only at the highest doses proposed. Brd4 BD1 is one of the two bromodomains present in the Brd4 protein and is used here as a comparative indicator of systemic bromodomain inhibition. Non-targeted bromodomain inhibitors have classically relied on sustained systemic concentrations over and above the Brd4 BD1 IC₉₀ to drive anti-inflammatory and anti-proliferative effects. Given the targeted nature of GSK3358699 and in contrast to prior clinical investigations with panBET inhibitors, GSK3358699 Brd4 BD1 IC₉₀ (128 ng/ml) will not be exceeded systemically at any dose planned.

[figure not shown]
Importantly, the potency advantage derived from the ESM ensures that even at these comparatively low levels of systemic BET inhibition, MCP-1 inhibition is expected to be essentially complete at doses greater than 20 mg GSK3358699 QD (Figure 5 and Table 2). Based on this modelling, the current anticipated GSK3358699 dose levels are considered appropriate to the objectives of this FTIH investigation.

Figure 4

GSK3358699 Predicted Human PK Profile

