10.1.2. Summary Measure

Continuous summaries of absolute values, percentage inhibition and predicted percentage inhibition will be presented for each biomarker detailed in Appendix 5, Section 13.5.4.

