13.9.9. Pharmacodynamic Tables

Part A

Phar	Pharmacodynamic (and or Biomarker): Tables								
No.	Population	IDSL / Example Shell	Title	Programming Notes	Deliverable [Priority]				
Solu	ble Inflammat	ory Mediators	•	•					
5.1.	Safety		Part A: Summary of Absolute Values and Percentage Inhibition of Soluble Inflammatory Mediators in Blood After Ex-Vivo LPS Activation	Page by Biomarker [S4] (note: this "[S4]" refers to the endpoint corresponding to this display; use the table in Section 13.5.4 for a list of biomarkers for each endpoint; applies to all PD displays).	SAC				
5.2.	Safety		Part A: Summary of Predicted Percentage Inhibition of Soluble Inflammatory Mediators in Blood After Ex-Vivo LPS Activation	Page by Biomarker [S4].	SAC				

Part C

Phar	Pharmacodynamic (and or Biomarker): Tables								
No.	Population	IDSL / Example Shell	Title	Programming Notes	Deliverable [Priority]				
Solu	ble Inflammat	ory Mediators							
5.3.	Safety		Part C: Summary of Absolute Values and Percentage Inhibition of Soluble Inflammatory Mediators in Blood After Ex-Vivo LPS Activation	Page by Biomarker [S4].	SAC				
5.4.	Safety		Part C: Summary of Predicted Percentage Inhibition of Soluble Inflammatory Mediators in Blood After Ex-Vivo LPS Activation	Page by Biomarker [S4].	SAC				

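### SAP 13.5.4 converts percentage inhibition with a formula valid only between 0 and 100%, has no rule for samples at or above baseline, and can report a rise as more than 100% inhibition

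*SAP*

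**What the plan says.** Under SAP 13.5.4, percentage inhibition in the TruCulture assay "is defined as the reduction from baseline in %, e.g. a 15% reduction from baseline would be a 15% inhibition". Call this z. No lower bound is given. The same section then introduces "The predicted percentage inhibition (y) in undiluted samples, to be calculated for selected biomarkers", and obtains it from z, measured in 3-fold diluted blood, by:

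y = 100 / [1 + (1/DF)^hill × (100 − z)/z]

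The constants are fixed: "where the dilution factor (DF) is equal to 3" and "Hill coefficient (hill) is equal to 1.4". The section derives the formula by assuming that the in vivo response follows the in vitro Emax curve, with equal ec50 "and the same hill coefficient and same Emax=1".

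On reporting, SAP 10.1.2 states: "Continuous summaries of absolute values, percentage inhibition and predicted percentage inhibition will be presented for each biomarker". The table in 13.5.4 assigns IL-6, MCP-1 and TNF to secondary objective S4. Table 5.2 is titled "Part A: Summary of Predicted Percentage Inhibition of Soluble Inflammatory Mediators in Blood After Ex-Vivo LPS Activation"; Table 5.4 is the Part C equivalent, and Listings 70 and 76 also show y. SAP 10.1.3 bases these analyses on the Safety population, and SAP 5.2 puts placebo first in the displays. SAP 5.3 sets the S4 baseline as the average of two pre-dose samples.

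**The concern.** An Emax model with Emax = 1 can only produce inhibition between 0 and 100%, so the conversion is meaningful only on that range. The z that the SAP feeds into it is not confined to that range: it is negative whenever a post-dose cytokine value exceeds baseline. With no drug effect, roughly half of placebo values should do so. Low doses and late time points are exposed too: protocol Table 2 predicts a maximum target engagement of only 9% at 1 mg, and in Part A the assay is sampled out to 48 h.

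I found no floor, exclusion or set-to-missing rule for z ≤ 0 in SAP 5.3, 10.1, 13.5.4 or 13.6. At stake is the placebo reference for one of the S4 summaries. Protocol 5.4 gives controlling the PD assessments as one reason for including placebo. A placebo column built from out-of-range conversions cannot do that.

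**Working it through.** **Inputs.** DF = 3 and hill = 1.4 (SAP 13.5.4). The protocol agrees on the slope (5.5.4, "Hill slope=1.4"): its IC50 of 4.8 ng/ml implies an IC90 of 4.8 × 9^(1/1.4) = 23.1, against 22.9 stated.

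**Reproducing the formula inside its range.** I generated z with ec50 = 4.8 and y with ec50 = 4.8/3 from the Emax model. At concentrations 1, 3 and 10, z = 10.01, 34.12 and 73.64, and y = 34.12, 70.68 and 92.86. The closed form returns the same y. The algebra is right for 0 < z < 100.

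**Outside its range.** Let c = (1/3)^1.4 = 0.2148. Multiplying out, y = 100z / [z(1 − c) + 100c].

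- Pole: z = −100c/(1 − c) = −21.48/0.7852 = −27.36%.
- Limit as z falls without bound: 100/(1 − c) = 127.4%. Every value beyond the pole is therefore above 100%.
- At z = 0 the formula as written divides by zero, although its limit is 0.

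| z (%) | y (%) |
|---|---|
| 90 | 97.7 |
| 50 | 82.3 |
| 10 | 34.1 |
| −5 | −28.5 |
| −10 | −73.4 |
| −20 | −346 |
| −25 | −1352 |
| −30 | +1445 |
| −40 | +403 |

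**Small example.** Take nine assumed placebo values of z: −30, −20, −10, −5, 3, 5, 10, 20, 27. Their mean is 0. The converted values sum to 1180, so mean y = 1180/9 = 131%. With y set to 0 where z ≤ 0, the mean is still 20%.

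**How often a placebo mean would be spoiled.** The documents give no assay or biological variability, so this rests on assumption. I took no drug effect, a log-normal ratio of post-dose to baseline, and 13 or 18 placebo values per time point. Eighteen is two Part A cohorts of 9, each participant receiving placebo once. Thirteen is the planned placebo number in Cohorts 4 and 5 (4 + 9). Results were nearly the same for both.

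| Log-ratio SD | Values beyond the pole | Mean y outside ±100% | Centre of median y |
|---|---|---|---|
| 0.05 | about 0% | about 0% | about 0% |
| 0.1 | 0.8% | 13% | about +1% |
| 0.2 | 11% | 43% | +21% |
| 0.3 | 21% | 49% | +46% |
| 0.4 | 27% | 52% | +62% |

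The true value in every row is 0. Setting y to 0 where z ≤ 0 leaves a placebo mean of +19%, +24% and +27% at SD 0.2, 0.3 and 0.4, because negative deviations are dropped while positive ones are amplified.

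**The case against.** A fair defence has four parts, and much of it stands.

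- **Role of y.** S4 is defined on cytokine concentrations, and SAP 10.1.2 plans three summaries. Tables 5.1 and 5.3 give absolute values and raw percentage inhibition without using the formula. A reader might infer that the S4 analysis as a whole is compromised; it is not.
- **Consequence.** The study tests no formal hypothesis, and the PD analysis is descriptive. The SAP was approved on 22 June 2020, after Cohort 5 was terminated on 18 March 2019, so no dose-escalation decision can follow from these tables. Listings 70 and 76 show absolute value, z and y together, where a reader could recognise +403% beside −40% as an artefact.
- **Certainty.** A reader might infer that every mean in Tables 5.2 and 5.4 will be meaningless. The documents do not support that. The result depends on a variability they do not state; at SD 0.05 the means are well behaved. Between −27.36% and 0, y stays finite and correctly signed, although increasingly magnified. Groups with clearly positive z are converted properly. That means are tabulated is itself inferred: the content of a continuous summary is set by a sponsor standard that is not reproduced, and table shells are kept separately.
- **Remedy.** A mixed model is not needed to close the gap; a domain rule would do that.

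What does not stand is the suggestion that this is only missing detail. Following the stated rule exactly can report a placebo rise as more than 100% inhibition. Nor does 13.5.4's restriction to selected biomarkers protect the tables, since 10.1.2 requires y for each one.

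**Conclusion.** The concern holds in a limited form. The out-of-range behaviour and the pole at −27.36% follow from the SAP's own constants and need no assumption. No rule handles z ≤ 0, and placebo is in the affected tables. How far a placebo mean is distorted does rest on assumption: negligible at log-ratio SD 0.05, a 13% chance of lying outside ±100% at 0.1, and 43–52% at 0.2–0.4. At 0.2–0.4 the median does not rescue the table either, centring at about +21% to +62% with no true effect. The exposed results are placebo, low doses and late time points in Tables 5.2 and 5.4, and individual values in Listings 70 and 76. Severity is moderate.

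**What to change.** **SAP 13.5.4.** State that y is calculated only for 0 < z < 100 and is otherwise shown as 'not calculable' in Listings 70 and 76.

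**Tables 5.2 and 5.4.** Do not average individual y values and do not floor them at zero. Convert the group-level percentage inhibition once per treatment and time point where it lies between 0 and 100%, and show 'not calculable' otherwise. Beside it, print the raw z summary and the number of samples with z ≤ 0, so that blank cells and small positive placebo values can be judged. Label the result as the conversion of a group value, because it is not the mean of individual conversions: for z = 10 and 50, mean y = (34.1 + 82.3)/2 = 58.2, while converting their mean of 30 gives 66.6.

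**Optional.** A model-based estimate of inhibition versus placebo, with a period term in Part A, is another way to obtain the group-level value.

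**Cost.** SAP wording and programming, with no new data. Tables 5.2 and 5.4 must be re-specified, and some cells will carry no predicted value.

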13.6. Appendix 6: Reporting Standards for Missing Data

13.6.1. Premature Withdrawals

Element	Reporting Detail
Element General	 A participant is considered to have completed: Part A (Cohorts 1 and 2) of the study if he has completed all the periods of Part A, including both follow-up visits. Part C of the study if he has completed all visits including both follow-up visits. Withdrawn participants may be replaced in the study. Additional replacement participants may be randomised to guarantee that sufficient participants are treated with GSK3358699 at any given dose before escalating to the following dose. Replacement participants will be assigned to the same treatment sequence (Parts A) or treatment (Part C) but have different subject numbers and randomisation numbers assigned. All available data from participants who were withdrawn from the study will be listed and all available planned data will be included in summary tables and figures, unless otherwise specified. Data from withdrawal visits will be listed. In Part C, Cohorts 4 and 5 were terminated prematurely while some subjects were part way through the treatment phase. Safety and PK data
	 collected after the date of termination in each cohort should not be included in summary tables/figures, but should be listed under a visit label of 'Early Termination'. The dates of termination were: Cohort 4: 14NOV2018
	• Cohort 5: 18MAR2019

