8.1. Adverse Events Analyses

The definition of an AE is detailed in Appendix 4 of the protocol.

Analyses of AEs will include all events, classified as in Section 13.3.

Adverse events analyses including the analysis of adverse events (AEs), Serious (SAEs) and other significant AEs will be based on GSK Core Data Standards.

Details of the planned displays are presented in Appendix 9: List of Data Displays.

207546

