13.3. Appendix 3: Study Phases and Treatment Emergent Adverse Events

13.3.1. Study Phases for Parts A and C

Assessments and events will be assigned to the relevant treatment Period dependent on whether they are spontaneous events (i.e. data collected in a log such as Adverse Events and Concomitant Medications, and Disposition) or planned events (i.e. data with timeslicing assigned such as ECG, Laboratory, and Vital Signs).

Spontaneous events are assigned to period according to the time of occurrence relative to the start date/time of the study treatment within the period up to, but not including, the start date/time of the study treatment in the next period. Planned assessments, including unscheduled visits are assigned to period according to the date of first visit of that period (including Day -1 and Day -10 assessments as applicable) up to the day prior to the first visit of the next period or day prior to Follow-Up visit (including Day -1 and Day -10 assessments as applicable).

For planned events, assessments prior to the date of first visit in Period 1 for Part A (or Period 7 for Part C) are assigned as Screening. For spontaneous events, events prior to the datetime of first dose in Period 1 for Part A are assigned as Pre-Treatment (or Period 7 for Part C).

For planned events, assessments on or later than date of first Follow-Up visit are assigned as Follow-Up. For spontaneous events, events later than date of last dose + 7 days are assigned as Follow-Up.

Study Phase	Definition
Prior	If medication end date is not missing and is before 28 days prior to
	screening visit
Concomitant	Any medication that is not a prior
1. NOTE:	

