13.3.1.1. Study Phases for Concomitant Medication

- Refer to Appendix 6: Reporting Standards for Missing Data for handling of missing and partial dates for concomitant medication. Use the rules in the table above if concomitant medication date is completely missing.
- Pre-trial medications are assumed concomitant if the stop date is within 28 days of the screening visit.

207546

13.3.2.	Trea	tment Emergent Flag for Adverse Events
Flag		Definition

Flag	Definition
Treatment Emergent	• If AE onset date is on or after treatment start date & on or before treatment stop date +1.
	 For crossover parts (Part A), if AE onset is during one period and worsens during a later period it would be counted in both periods. For the initial period the logic would be as above. For the later period the logic would use the treatment dates associated with the later period:
	Treatment Period Start Date \leq AE Worsening Date \leq Study Treatment Stop Date + 1 days.

NOTES:

- If the AE start/worsening date is on or after treatment start date, and treatment stop date is missing, then the AE will be considered to be Treatment Emergent.
- Time of study treatment dosing and start/stop time of AEs should be considered, if • collected.

207546

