13.6.2. Handling of Missing Data

Element	Reporting Detail
General	• Missing data occurs when any requested data is not provided, leading to
	blank fields on the collection instrument:
	• These data will be indicated by the use of a "blank" in participant
	listing displays. Unless all data for a specific visit are missing in
	which case the data is excluded from the listing.
	• Answers such as "Not applicable" and "Not evaluable" are not
	considered to be missing data and should be displayed as such.

207546

Element	Reporting Detail
General	• Partial dates will be displayed as captured in participant listing displays.
Adverse Events	 The eCRF allows for the possibility of partial dates (i.e., only month and year) to be recorded for AE start and end dates; that is, the day of the month may be missing. In such a case, the following conventions will be applied for calculating the time to onset and the duration of the event: Missing Start Day: First of the month will be used unless this is before the start date of study treatment; in this case the study treatment start date will be used and hence the event is considered On-treatment as per Section 13.3. Missing Stop Day: Last day of the month will be used, unless this is after the stop date of study treatment; in this case the study treatment stop date will be used. Completely missing start or end dates will remain missing, with no imputation applied. Consequently, time to onset and duration of such events will be missing.
Concomitant Medications	 Partial dates for any concomitant medications recorded in the CRF will be imputed using the following convention: If the partial date is a start date, a '01' will be used for the day and 'Jan' will be used for the month If the partial date is a stop date, a '28/29/30/31' (last day of the relevant month) will be used for the day and 'Dec' will be used for the month. The recorded partial date will be displayed in listings.

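### SAP 13.6.1 removes Part C safety data after the cohort termination dates from all summaries, contradicting SAP 8.1 and 8.2 and undeclared in 2.1

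*SAP*

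**What the plan says.** SAP 13.6.1 records that Cohorts 4 and 5 ended early while some "subjects were part way through the treatment phase. Safety and PK data" and continues "collected after the date of termination in each cohort should not be included in summary tables/figures". These data are to be listed under an Early Termination visit label. The dates are 14NOV2018 (Cohort 4) and 18MAR2019 (Cohort 5). No exception is named for AEs, SAEs, or worst-case and maximum tables.

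The same section says of ordinary withdrawals that "all available planned data will be included in summary tables and figures, unless otherwise specified".

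SAP 8.1 says "Analyses of AEs will include all events, classified as in Section 13.3". SAP 8.2 says that laboratory analyses cover every post-baseline assessment, with unscheduled visits kept to listings. SAP 2.3 confirms that only Cohorts 4 and 5 were dosed in Part C. SAP 2.1, the table of changes from the protocol, lists only the analysis populations; its closing text adds the exploratory analyses and Part B.

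On partial AE dates, SAP 13.6.2.1 says that for a missing stop day "Last day of the month will be used, unless this is after the stop date of study treatment"; in that case the treatment stop date is used.

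**The concern.** Safety and tolerability is the primary objective, and Part C is the only repeat-dose evidence. A calendar cut-off that sends later safety data to listings takes out exactly the scheduled post-treatment observation of the participants who were stopped. If events started after the cut-off, the Part C incidence tables would be too low. How long each participant is observed in the summaries would depend on where he stood on a fixed date, not on a rule tied to his dosing.

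Two programmers could also produce different primary-endpoint tables from the same SAP, one following 8.1 and 8.2, the other following 13.6.1.

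**Working it through.** **Step 1. The passages side by side.** The plan contains no figure to reproduce here, so the main check is textual.

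| Place | Part C safety data after the cut-off |
|---|---|
| SAP 13.6.1 | Out of tables and figures; listed |
| SAP 8.1 | All AEs analysed |
| SAP 8.2 | All post-baseline laboratory assessments analysed, except unscheduled visits |
| SAP 13.3.1 | AEs assigned by time of occurrence, with their own Follow-Up phase |
| SAP 13.9.5, Table 2.23 | Titled as covering all AEs; no cut-off in the programming note |
| Protocol 9.2.1 | AEs collected until the follow-up visit |
| Protocol 10.4.1 | Safety Population; no calendar cut-off |
| SAP 2.1 | Rule not declared |

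Section 13.6.1 is the more specific text and would probably govern visit-based data. For AEs the conflict is unresolved.

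**Step 2. Scheduled data that leave the summaries.** Follow-up 1 falls 7 to 14 days after the last dose. The protocol schedules (2.3 and 2.4) place vital signs, ECG, haematology, coagulation, chemistry and urinalysis there. For anyone dosed up to the termination date, this visit falls at least 7 days after the cut-off. GGT and CK are scheduled only at screening, Day -1 and follow-up (SAP 8.2, note 4). A Cohort 5 participant followed up after 18MAR2019 therefore has no scheduled post-baseline GGT or CK value in Table 2.31. The rule also reaches participants who had finished dosing but whose follow-up came after the date.

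**Step 3. Scale, under stated assumptions.** Assume the last dose is on Day *d*, that this is the termination date, and that follow-up lasts *f* = 7 to 14 days. Share of the AE collection window outside the summaries = *f* / (*d* + *f*).

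| Stopped on | *f* = 7 | *f* = 14 |
|---|---|---|
| Day 4 | 7/11 = 64% | 14/18 = 78% |
| Day 7 | 7/14 = 50% | 14/21 = 67% |
| Day 13 | 7/20 = 35% | 14/27 = 52% |

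This is a share of time, not of events.

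**Step 4. What one excluded event would do.** Protocol 10.2.1 uses a flat Beta(1,1) prior. Its example of 1 event in 6 gives Beta(2,6), 95% interval 0.037 to 0.579, which reproduces its 0.04 to 0.58. Actual numbers dosed are not given, so planned active numbers are used: 9 in Cohort 5, and 10 + 9 = 19 for Cohorts 4 and 5, which SAP 5.2 pools under one label.

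| Active n | 0 events | 1 event |
|---|---|---|
| 9 | 0.003 to 0.308 | 0.025 to 0.445 |
| 19 | 0.001 to 0.168 | 0.012 to 0.249 |

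**Step 5. The stop-day rule.** Take an AE starting *k* days after the last dose, with an unknown stop day. The end of its stop month falls after treatment stop, so the imputed stop date becomes the treatment stop date, *k* days before onset. SAP 13.6.2.1 uses these imputations for time to onset and duration only, so incidence is unaffected.

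**The case against.** The strongest defence is that 13.6.1 was written for visit data. It works through a visit label, whereas AEs are log records placed by time of occurrence. SAP 8.1 and the title of Table 2.23 point to all AEs being summarised. Assessments made after an abrupt stop may not fit nominal visits, which is the only basis for summaries (SAP 13.2.1), and unscheduled visits are already kept out of tables (SAP 13.4.2). The study is descriptive, the cut-off applies to both arms alike, and the excluded data are to be listed.

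Much of this stands. It is an ambiguity for AEs, not a settled omission. The argument does not rescue scheduled follow-up visits, which are neither unscheduled nor off the nominal grid. Listing is also a partial remedy: the planned Part C laboratory, ECG and vital-sign listings for numeric results (51-52, 59-60, 63-64) are confined to abnormal values or to participants who have one.

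A reader might infer more than the documents support:

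- *That 13.6.1 contradicts the rule for ordinary withdrawals.* That rule carries its own exception for what is otherwise specified, and the termination bullet is such a specification. The two treat participants differently but do not contradict each other.
- *That nothing after the last dose is summarised.* Results on or before the termination date stay in. Holter Tables 2.41-2.42 are untouched, because Holter monitoring is at screening only (protocol 9.4.5).
- *That the arrhythmias behind the Cohort 4 hold are dropped.* Amendment 4 describes a hold to review events already observed. On that account they came before the stop. No passage shows an event after either date.
- *That the treatment-emergent window also truncates AE tables.* SAP 13.3.2 ends it "on or before treatment stop date +1", while under 13.3.1 "events later than date of last dose + 7 days are assigned as Follow-Up". These are different constructs, and no planned AE table or figure is restricted to the treatment-emergent flag. The mismatch removes nothing.

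**Conclusion.** The concern holds as a conflict on the primary endpoint that must be resolved. As written, 13.6.1 covers all dosed Part C participants, contradicts 8.1 and 8.2, and is not declared in 2.1. Its effect on scheduled follow-up laboratory, ECG and vital-sign results needs no contested reading. Its effect on AEs depends on which passage a programmer follows.

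Incidence could be understated; that it is understated cannot be shown. The 50% to 67% for a Day 7 stop rests on the last dose falling on the termination date and on 7 to 14 days of follow-up. The interval comparison rests on planned, not actual, numbers. The real effect cannot be computed without the numbers stopped and the events recorded after each date.

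The stop-day imputation is a minor, separate error, confined to AE duration.

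**What to change.** Reword SAP 13.6.1 as follows:

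- Part C AE Tables 2.23-2.30 and Figure 2.2 include all AEs to final follow-up, whatever the termination date.
- Worst-case and maximum Tables 2.32, 2.33, 2.35, 2.36, 2.38, 2.39 and 2.44, and the summaries at the follow-up visit, include scheduled follow-up assessments whatever the termination date.
- The Early Termination exclusion applies only to off-schedule assessments in by-nominal-visit summaries, in line with the existing unscheduled-visit rule.

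Declare any cut-off that remains in SAP 2.1, with its reason. In 13.6.2.1, require that an imputed AE stop date never precedes onset, for example by capping it at final follow-up instead of treatment stop. No change to the treatment-emergent window is needed on this account.

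The cost is SAP wording and minor programming. The data are already collected.
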